Methods: Adult patients presenting for endoscopic closure of a gastrointestinal luminal defect will be enrolled and randomized 1:1 to closure of the defect with either the X-Tack system (the study group) or the Overstitch system (the control group.) Demographics, comorbidities, laboratory values, size of defect, time to close the defect, and the number of sutures to close the defect will be recorded. The primary outcome will be the time to closure of the defect. Secondary outcomes will include the rate of incomplete closures (as defined as either crossover to the other study group per endoscopist's discretion, or the need for additional modalities to close the defect such as endoscopic clips) as well as complications (bleeding, infection, perforation) and costs. Time to closure will be compared using the student T-test. To detect a 5-minute mean difference between the two groups at 80% power with an alpha of 0.05 and 1:1 randomization, 16 patients will be required in each group. Anticipating loss of subjects or data for technical or unanticipated reasons after randomization, we expect that 50 patients will need to be enrolled.

A. Specific Aims

The primary objective of the study is to compare the time required to close a defect or fistula in the gastrointestinal tract between the X-Tack system and the current standard of care (suturing with the Overstitch system.) The secondary objectives of the study will be to compare the rate of incomplete closures (as defined as either crossover to the other

study group per endoscopist's discretion, or the need for additional modalities to close the defect such as endoscopic clips) as well as complications (bleeding, infection, perforation) and costs between the X-Tack system and the current standard of care. We hypothesize that the X-Tack system will permit faster closure of endoscopic defects compared to the current standard, because the X-Tack does not require a different endoscope to use.

B. Background and Significance

Perforation rates with endoscopic submucosal dissection (ESD) of colonic lesions and early cancers can be as high as 4% with delayed bleeding rates up to 8%. Endoscopic closure of resection defects has been shown to reduce delayed bleeding rates in the colon and is the least invasive method for closure of perforations or fistulas. Current options for closure include through-the-scope (TTS) clips, over-the-scope clips (OTSC,) and endoscopic suturing with the Overstitch system. TTS clips frequently misdeploy or are dislodged during complex closures and are cumbersome for the closure of large defects. OTSC are limited to closure of ~2 cm defects but are unable to capture the entirety of larger defects. The Overstitch system can close defects of any size but requires the use of a double-channel endoscope that is wide in diameter and is often too short to reach the right colon. It also requires removal of the endoscope that is being used for the resection from the patient in order to introduce the double-channel scope for closure. The X-Tack system offers the ability to close large defects with endoscopic sutures but can be introduced through the instrument channel of any standard endoscope, filling the gap between clips and suturing.

[figure not shown]
C. Preliminary Studies/Progress Report

The X-Tack is currently FDA cleared on the basis of similarity to previous suturing devices, though human data is pending. Preclinical animal data primarily compared the X-Tack to through-the-scope (TTS) clips. In the 24 X-Tack cases, 21 could be closed with just one X-Tack device, while a second device was used in 3 cases. Technical closure of defects in the animal model was successful in 24/24 cases using the X-Tack, versus just 13/16 cases using TTS clips. On necropsy, the time to complete healing of the defects was comparable between the X-Tack and TTS clip cases. On this basis, the investigators concluded that the X-Tack achieved expected levels of tissue healing and higher technical success rates than the current standard of care.

D. Research Design and Methods

Currently, the community standard is that gastroenterologists who are familiar with Overstitch start using the X-Tack without additional training. However, a hands-on demonstration session with the X-Tack device in a "dry lab" has been conducted with each endoscopist in the trial prior to the study in order to familiarize them with device before enrollment. Each endoscopist has also participated in a "wet lab" using an explant (porcine stomach) to simulate in vivo closure of defects using the X-Tack system. The device operates in a similar fashion compared to previous suturing devices, which are

used frequently by all endoscopists involved in this study. On this basis, all endoscopists in the study report comfort and familiarity with the X-Tack system, and the “break-in” period is not anticipated to affect safety or results during the study. The primary study visit will be comprised of the endoscopic procedure at the time of defect closure and a telephone call 48-72 hours later to assess for complications. Patient will be enrolled in the pre-procedure area. If the patient has a pre-procedure visit, they may be notified of their potential for enrollment in the study at that time, though not all patients have a pre-procedure visit in our practice. Patients will be randomized to closure with the X-Tack system versus closure with the Overstitch system prior to their procedure using a centralized computer-generated randomization. Technical success of closure, time of closure, number of sutures required, need for alternative modalities for closure, and any intraprocedural complications (bleeding, perforation) will be recorded. Any patient with possible periprocedural perforation will receive antibiotics at the endoscopist’s discretion. At the endoscopist’s discretion, the patient may cross over during the procedure to the other group if they believe that their current closure strategy is failing to safely close the defect. Alternate methods of closure (TTS clips, over-the-scope clips) may be used in either group if required by the endoscopist for safe closure of the defect. After the procedure, most patients are observed in the recovery area for 1-2 hours for any signs of complications before they are discharged home.

E. Statistical Methods

Time to closure will be compared using the student T-test. To detect a 5-minute mean difference between the two groups at 80% power with an alpha of 0.05 and 1:1 randomization, 16 patients will be required in each group (32 patients in total.) Anticipating loss to follow-up and patient dropout, we expect that a total of 50 patients will be required. Categorical variables will be compared using the chi squared test.

F. Gender/Minority/Pediatric Inclusion for Research

Women and minorities will be included in the research protocol.

G. Human Subjects

1. Provide number, age range, and health status of the subject population. List criteria for inclusion or exclusion.

We anticipate enrolling 50 patients in total.

Inclusion criteria: Patients > 18 years of age undergoing closure of a gastrointestinal luminal defect for which a suturing device would be otherwise indicated.

Exclusion criteria: INR > 2, platelets < 150, ongoing anticoagulation not meeting ASGE Antithrombotic Guidelines (Acosta RD et al, The Management of Antithrombotic Agents for Patients Undergoing GI Endoscopy, Gastrointest Endosc, 2016; 83(1): 3-16,) hemodynamic instability, ongoing or anticipated pregnancy

2. Identify sources of research material in the form of specimens, records or data.

Records and data will include chart data including demographics and comorbidities, laboratory values, endoscopy reports, and video acquired during endoscopy.

3. Describe plans for recruitment and consent procedures to be followed.

The endoscopist performing the procedure will meet the potential subject in the pre-procedure holding area. The endoscopist will review the consent documents with the potential subject. The subject will be provided time to review the entirety of the document and ask any questions of the endoscopist that they have. If they are amenable to proceeding, they will sign the consent and the procedure will be performed. No additional recruitment or inducement (i.e. advertising) is anticipated.

4. Describe risks and assess likelihood and seriousness.

The primary potential risk of this research is device failure (i.e. failure to close defect or complications of closure, such as bleeding or perforation.) Device failure is expected to be uncommon. Most device failures are expected to be minor (i.e. perhaps requiring an additional device to complete closure of the rest of the defect, but no immediate harms or risks to the patient besides longer procedure time.) Serious complications (i.e. bleeding or perforation attributable to the device and requiring hospitalization) are expected to be very rare.

5. Describe procedures for protecting against or minimizing potential risks.

Because the research device will be used for defect closure during the same period of sedation as the current standard of care, participants should not perceive any difference in their procedure beyond signing an additional consent form. Patients with a propensity for bleeding i.e. thrombocytopenia or coagulopathy will be excluded to avoid adverse events.

6. Describe potential benefits and importance to the subjects and others.

Participants could potentially benefit from a faster defect closure with reduced anesthesia time. The ease of deployment of the X-Tack device also might make clinical success more likely. If the X-Tack device proves to be a faster, safer way to close mucosal defects or fistulas, future patients undergoing endoscopic submucosal dissection or fistula closure could benefit from less anesthesia time and a better chance at clinical and technical success.

7. Discuss why risks are reasonable in relation to benefits.

The risks and side effects of closure with the X-Tack system are anticipated to be identical to those of the Overstitch system. Given that the Overstitch is the current standard of care, and the X-Tack is anticipated to be faster and more user-friendly, the benefits of introducing the X-Tack outweigh the risks.

H. Data and Safety Monitoring Plan

1. Data and Safety Monitoring Plan (DSMP)

a. reporting mechanisms for adverse events to the IRB, FDA, and NIH.

Adverse events will be tracked and reported to the IRB at the time of interim analysis and final analysis (anticipated study time is less than one year.) Adverse events will be defined as bleeding, infection, or perforation occurring within 72 hours of the procedure. Severe adverse events will be reported to the IRB at the time of occurrence. Adverse events will be defined using the ASGE Adverse Event Lexicon (Cotton PB et al, A lexicon for endoscopic adverse events: report of an ASGE workshop. *Gastrointest Endosc*, 2010; 71(3): 446-454.) Severe adverse events in this lexicon are considered any adverse events resulting in hospital admission >10 days, ICU admission > 1 night, surgery for an adverse event or permanent disability. Severe adverse events will be reported using the OHR online portal.

b. adverse event (AE) grading

Adverse events will be graded according to the ASGE adverse event lexicon.

c. plan for unanticipated AE reporting

Severe adverse events will be reported to the IRB at the time of occurrence.

d. plan for annual reporting of AEs

The anticipated study time is less than one year, thus all reporting will occur at the time of interim analysis and final analysis.

e. interim efficacy analysis where appropriate

Perforation rate and complications related to inadequate closure (leak, fistula, peritonitis, bleeding) will be monitored. Perforation or complications related to inadequate closure > 50% compared to control group will lead to

stoppage of the trial. Interim analysis will be performed at the midpoint of enrollment (25 patients.) For instance, if after 25 patients have enrolled, 2 patients in the control group experience a complication, yet 4 experience a complication in the X-Tack group, the results will be reviewed with the independent safety monitor for possible stoppage of the trial pending discussion with the IRB.

2. If applicable, describe the Data and Safety Monitoring Board (DSMB) that will be responsible for monitoring the study.

An independent reviewer has been selected within the Jefferson Division of Gastroenterology who is outside of the investigator group who will review the interim analysis.

I. Literature Cited

2. Pohl H, et al. Clip Closure Prevents Bleeding After Endoscopic Resection of Large Colon Polyps in a Randomized Trial. *Gastroenterology* 2018;157:977-984.

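### Read literally, the incomplete-closure outcome scores a defect left open as complete when the endoscopist neither crosses over nor adds another modality

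*Combined protocol and SAP*

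**What the plan says.** The Methods summary and A. Specific Aims give the same definition of the first-listed secondary outcome. Incomplete closure is either crossover at the endoscopist's discretion or "the need for additional modalities to close the defect such as endoscopic clips". No third trigger is given.

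D. Research Design and Methods makes both steps a matter of judgement. On crossover it says "the patient may cross over during the procedure to the other group if they believe that their current closure strategy is failing". Clips of either kind are likewise allowed in both arms when the endoscopist considers them required. The same section lists the procedural data to be recorded: "Technical success of closure, time of closure, number of sutures required, need for alternative modalities for closure". Technical success is not defined there or elsewhere, and it is not named in any primary or secondary outcome.

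G. Human Subjects, item 4, describes the main research risk as "device failure (i.e. failure to close defect or complications of closure, such as bleeding or perforation". It then says that most failures should be minor and gives as an example "perhaps requiring an additional device to complete closure of the rest of the defect".

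E. Statistical Methods gives a total enrolment of 50 with 1:1 allocation and a chi-squared test for categorical variables. It gives no expected rate and no power for incomplete closure.

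**The concern.** An outcome called incomplete closure should turn on whether the defect was closed. As written, it turns on whether the operator escalated. The two usually go together, but not always: an endoscopist may accept a residual gap and stop. That patient meets neither trigger and enters the analysis as a complete closure, although the risk section would call the same result a device failure.

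Apart from closure time, this is the only listed outcome that measures how well the devices work. The endoscopist handles the device, knows the arm, and decides whether to cross over or add clips. An outcome built only on those decisions reflects readiness to escalate as well as closure. If that readiness differs between arms, the comparison of rates is distorted. The time result also needs a sound measure of closure beside it to be interpretable.

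**Working it through.** The plan states no figure for this outcome, so there is none to reproduce. The sample size of 16 per group is for time to closure and does not bear on the point. The check is mainly a comparison of sections.

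**1. Apply the definition to each possible end state.**

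| Defect at end of procedure | Crossover | Other modality | Score under Methods summary / section A | Status under section G, item 4 |
|---|---|---|---|---|
| Closed | No | No | Complete | Not a failure to close |
| Closed | Yes | No | Incomplete | Assigned device did not finish the closure |
| Closed | No | Yes | Incomplete | Assigned device did not finish the closure |
| Open | Yes, or other modality tried | | Incomplete | Device failure |
| Open | No | No | **Complete** | **Device failure** |

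Only the last row conflicts: the outcome and the risk section classify the same patient in opposite ways.

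**2. Can the last row occur?** Yes. Section D permits crossover and added modalities but requires neither, so an open defect does not automatically trigger either one.

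**3. Does another outcome pick it up?** Technical success would be the natural place, and section D records it. However, no outcome in the Methods summary, section A or section E uses it.

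**4. Size.**
- Patients per arm: 50 / 2 = 25.
- Effect of one misclassified patient on that arm's rate: 1/25 = 4 percentage points.
- For k such patients in one arm: k × 4 points, so 2 give 8 points and 3 give 12 points.
- If only the 16 per group from the sample-size statement were evaluable, one patient would be 1/16 = 6.25 points.

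The value of k is unknown. The documents give no rate of defects left open for either device, so no expected bias can be calculated.

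**The case against.** **The word used is need, not use.** The definition and the data list in section D both refer to a need for other modalities. An open defect could be read as an unmet need, and so as incomplete. This is the best counter-argument, and it may be what the authors intend. But the text does not say so, and a coordinator filling in the form could reasonably record no need when nothing further was tried.

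**Endoscopists will normally escalate.** Section D provides for crossover when the strategy is failing and for other methods when required, so the uncounted case may be rare. That is fair, and nothing in the documents shows otherwise. It limits the likely size but does not close the gap.

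**Harm from a residual gap is caught elsewhere.** H. Data and Safety Monitoring Plan monitors complications of inadequate closure, and complications are a secondary outcome. That covers some clinical consequences, with adverse events defined within 72 hours. It does not record whether the defect was closed.

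**A reader might infer more than the documents support.** Three stronger readings should be set aside:
- *That the risk section contradicts the outcome over a second X-Tack.* The additional device in section G, item 4, may mean clips or the other suturing system, which the outcome already counts. The wording is also an illustration of risk, not an outcome definition.
- *That the animal data size the problem.* C. Preliminary Studies/Progress Report says "21 could be closed with just one X-Tack device, while a second device was used in 3 cases". All 24 were technically successful closures, so 3/24 says nothing about defects left open. The comparator was clips, so there is no Overstitch rate either.
- *That an arm leaving gaps would also look faster.* A defect never closed has no closure time, and the plan does not say how such a patient enters the t-test. The direction of any effect on time is therefore unknown.

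**Conclusion.** The point holds for defects left open. The two-trigger definition, read literally, can score a failure to close as a complete closure. This is a stated rule that can misclassify patients in the first-listed secondary outcome, not merely a missing detail.

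The size is 4 percentage points per misclassified patient, assuming 25 analysed per arm. Nothing further can be quantified. The conclusion rests on taking the two triggers as exhaustive and on not stretching need to cover an open defect for which nothing more was tried. The primary outcome's sample size is unaffected, and no stated figure is overturned. The documents do not establish that second-unit use is a failure the outcome misses.

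**What to change.** Before outcome data are reviewed, amend the Methods summary and section A so that incomplete closure means any of:

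1. a residual open defect at the end of the procedure (technical failure);
2. crossover to the other device;
3. an additional closure modality.

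Report each component by arm alongside the composite. In section D, define technical success as the absence of item 1, so that the item already recorded feeds the outcome.

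Optionally, report use of a second unit of the same device as a separate descriptive line in both arms, without counting it as incomplete, and clarify in section G, item 4, what an additional device means.

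The main change costs only wording, because technical success is already recorded. The optional line may need a device-count field, since the plan lists the number of sutures but not of devices. The downside is a slightly higher reported incomplete-closure rate.

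### For defects made in the same session, randomisation before the procedure lets the endoscopist know the closure device while creating the defect that is later timed

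*Combined protocol and SAP*

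**What the plan says.** - **Timing of allocation (section D).** "Patient will be enrolled in the pre-procedure area", and "Patients will be randomized to closure with the X-Tack system versus closure with the Overstitch system prior to their procedure". The method is central and computer-generated.
- **Who is present (section G.3).** "The endoscopist performing the procedure will meet the potential subject in the pre-procedure holding area". The same person takes consent, and the procedure follows once it is signed. No section says when that person learns the arm, and none describes masking or holding the allocation back.
- **How defects arise (sections A and B).** The objective is to "compare the time required to close a defect or fistula in the gastrointestinal tract", so both resection defects and fistulas are in scope. Section B says of Overstitch: "It also requires removal of the endoscope that is being used for the resection from the patient". That describes closure following resection in one session.
- **Eligibility (section G.1).** Patients must be "undergoing closure of a gastrointestinal luminal defect for which a suturing device would be otherwise indicated".
- **Outcome and analysis (Methods summary and section E).** The primary outcome is time to closure, compared by Student's t-test with no covariates. The Methods summary lists "size of defect, time to close the defect, and the number of sutures to close the defect will be recorded", but defect size has no role in the randomisation or the analysis.

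**The concern.** Randomisation balances what exists when the arm is assigned. A fistula exists then; a defect that is still to be resected does not. In a same-session resection the person who creates the defect also closes it, and that closure is the primary endpoint. If this person already knows the device, the extent, technique or position of the resection can be planned around it, without any intent to favour an arm. Section B gives a reason why planning might differ: the endoscope needed for Overstitch is wide, is often too short for the right colon, and requires a scope exchange, whereas X-Tack passes through a standard endoscope.

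A difference in closure time could then partly reflect different defects rather than different devices, in either direction. This would arise even if every randomised patient were closed and analysed as assigned. Adjusting for recorded size would not cleanly remove it, because size measured after allocation may itself be affected by arm.

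**Working it through.** **1. Order of events for a same-session resection.** Enrolment and consent in the pre-procedure area (D, G.3); randomisation before the procedure (D); resection; defect exists; closure is timed. The defect comes after allocation. For a fistula or an existing perforation, the defect comes before allocation and knowing the arm cannot change it.

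**2. The plan's own sample size.** Inputs from section E: difference 5 minutes, power 80%, alpha 0.05, 16 per group. No SD is given and sidedness is not stated, so the 16 cannot be reproduced directly. Solving for the SD, two-sided:

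- Normal approximation: SD = 5 × √(16/2) / (1.960 + 0.842) = 14.14 / 2.802 = 5.05 minutes.
- Exact t-test (non-central t, 30 degrees of freedom): SD = 4.88 minutes.

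The illustration uses 4.88, and an assumed 8 as a less favourable value.

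**3. Effect of an arm-related shift in defect difficulty.** Let b be the difference between arms in mean closure time that is due only to different defects, averaged over all patients, with no true device effect. The t-statistic is then non-central with parameter b / (SD × √(2/n)) and 2n − 2 degrees of freedom. The two-sided critical values are 2.042 (n = 16) and 2.011 (n = 25). The shifts of 1 and 2 minutes are assumptions, equal to 20% and 40% of the 5-minute target.

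| SD (min) | n per arm | b (min) | Non-centrality | False-positive rate |
|---|---|---|---|---|
| 4.88 | 16 | 1 | 0.58 | 8.7% |
| 4.88 | 16 | 2 | 1.16 | 20.2% |
| 4.88 | 25 | 1 | 0.72 | 10.9% |
| 4.88 | 25 | 2 | 1.45 | 29.5% |
| 8 | 16 | 1 | 0.35 | 6.4% |
| 8 | 16 | 2 | 0.71 | 10.5% |
| 8 | 25 | 1 | 0.44 | 7.2% |
| 8 | 25 | 2 | 0.88 | 13.9% |

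With b = 0 every row would be 5%. The 25-per-arm rows assume that all 50 enrolled patients are analysed. For a fixed b the rate rises with n, so enrolling more patients does not dilute the bias.

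**4. Dilution by pre-existing defects.** If a share p of patients have defects made after allocation, and the shift in those patients is s, then b = p × s. If half the cases were fistulas or existing perforations (an assumption), an average of 1 to 2 minutes would need s = 2 to 4 minutes in every resection case, or 40-80% of the target difference.

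**The case against.** The strongest reply is that the mechanism is inferred at each step.

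- The trial enrols patients for closure of a defect, and the scope-exchange sentence in section B is background rather than a study procedure. A reader might take section G.6 to make same-session resection the trial's target use. It does not: it speaks of future patients who might benefit, and it names fistula closure as well. This stands. Same-session resections fit the eligibility wording, but their share is unknown.
- A reader might infer that the endoscopist is told the arm before resecting. Section D says when patients are randomised, not when the operator is informed. This stands as a limit, but the silence is also the gap, because nothing prevents early knowledge.
- A reader might treat defect size as the main driver of closure time. No passage says so. It is a plausible assumption and no more.
- The false-positive rates rest on an invented shift averaged over all patients. At the low end (1 minute, SD 8, 16 per arm) the rate is 6.4% against 5%, which is small. This stands.
- Defect size is recorded, and section G.2 lists endoscopy reports and video, so an imbalance between arms could be seen. That is a useful diagnostic, but it does not repair the comparison.
- Late allocation could do harm of its own. The protocol does not define when timing starts, so device set-up could move into the timed interval differently by arm. Permitted crossover implies that both systems must be obtainable, not that both are equally ready. This stands, and the fix has to deal with it.

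**Conclusion.** The concern holds, limited to defects created after allocation. For those, the plan lets an unmasked endoscopist know the device while making the defect that will be timed, and the unadjusted primary test cannot separate a device effect from a defect effect. The documents do not support the stronger reading that the whole primary comparison is biased, or that operators would in fact tailor their resections. Pre-existing fistulas and perforations are unaffected, and the case mix, direction and size of any bias are not given.

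The ranges of 9-20% and 11-30% (SD 4.88 minutes, 16 and 25 per arm) and of 6-11% and 7-14% (SD 8 minutes) are illustrations. They rest on an assumed average shift of 1 to 2 minutes, on assumed SDs, on a two-sided test, and on defect size affecting closure time. The average shift is smaller in proportion to the share of pre-existing defects. The change is still worth making, because it closes this route at little cost and makes defect size a true pre-allocation variable.

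**What to change.** In section D, replace the sentence on timing with wording such as:

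> Consent is obtained before the procedure. The central allocation is opened only after the defect has been created or exposed, its size has been recorded, and the endoscopist has confirmed that closure with a suturing device is indicated. Closure time starts at one defined event that is the same in both arms. Time spent obtaining the allocation is not counted.

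The investigators need to name the clock-start event and say whether device set-up and scope exchange fall inside the interval, since the hypothesis in section A rests on X-Tack not needing a different endoscope. Without that definition, late allocation could itself add time to one arm.

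If allocation has to stay before the procedure, the protocol should at least state when the endoscopist learns the arm and commit to reporting defect type, size and location by arm.

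Cost: protocol wording and one request to the existing central randomisation during the procedure. The downside is a short pause, and the assigned device cannot be set up ahead. The sample size does not change.

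### The primary t-test ignores defect size and indication in a mixed population; a prespecified model with a few covariates would protect precision at little cost

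*Combined protocol and SAP*

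**What the plan says.** The Methods summary states: "The primary outcome will be the time to closure of the defect". Section E gives the primary analysis in one sentence: "Time to closure will be compared using the student T-test". No covariate, stratum or endoscopist term appears there or elsewhere.

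Section A sets the objective as to "compare the time required to close a defect or fistula in the gastrointestinal tract", so fistulas and other defects are pooled. Section G.1 admits any luminal defect that would otherwise be sutured, with no limit on type, site or size. Section B speaks of resection defects, perforations and fistulas as targets for closure. Section D refers to more than one endoscopist and does not say how many.

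Section D places randomisation before the procedure, "using a centralized computer-generated randomization", and names no stratum, block or minimisation factor. The Methods summary lists defect size among the recorded data. Defect type is not on that list.

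The sample size in section E is set "To detect a 5-minute mean difference between the two groups at 80% power with an alpha of 0.05 and 1:1 randomization", giving 16 per group and 32 in total, with 50 to be enrolled. No SD is given.

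**The concern.** Closure time plausibly depends on how large the defect is, what kind it is and who closes it. The protocol itself gives reasons to expect variation: section B notes that the control system's endoscope may not reach the right colon, and that its use after a resection requires an endoscope exchange, a step that a fistula closure without resection may not share.

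Variation from such sources goes into the error term of an unadjusted t-test. It widens the confidence interval and leaves the observed difference open to chance imbalance between two small arms. If an imbalance appears and no model was prespecified, any later adjustment will look post hoc. The plan collects the most obvious covariate, defect size, and then leaves it out of the analysis.

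**Working it through.** **1. The plan's own figure.** Inputs from section E: difference 5 minutes, power 80%, alpha 0.05 (taken as two-sided), 1:1. The SD is missing, so 16 per group cannot be reproduced from stated inputs, only back-solved.
- Normal approximation: n = 2(1.96 + 0.84)² × (SD/5)². At SD 5 this is 2 × 7.85 × 1 = 15.7, which rounds up to 16.
- Noncentral t: 16 per group gives 80% power at SD 4.88. At SD 5, power is 78% with 16 per arm and 93% with 25 per arm.

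SD 5 is therefore used below as an assumed total SD.

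**2. Power with one two-level type factor in the model.** Assumptions: total SD 5, effect 5 minutes, 32 analysed, no stratification. The share of variance explained by type is not in the documents, so a range is shown.

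| Variance explained by type | t-test | Adjusted |
|---|---|---|
| 0% | about 78% | about 77% |
| 5% | about 78% | 79% |
| 10% | about 78% | 81% |
| 20% | about 78% | 85% |
| 30% | about 78% | 90% |

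With 50 analysed the t-test starts at about 93%, so little remains to be gained.

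**3. If the mixed population is more variable.** At total SD 8 and 25 per arm the t-test has 58% power. Using SD × √(1 − R²), this becomes 68% at R² = 0.2 and 74% at R² = 0.3. That shortcut ignores the degrees of freedom spent on covariates, so these two figures are slightly optimistic.

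**4. Chance imbalance.** Take a type with 30% prevalence and 25 patients per arm. A gap of 20 percentage points is 5 patients (5/25). With independent binomial counts in each arm, P(|X₁ − X₂| ≥ 5) = 0.164, about 16%.

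The shift this causes depends on the gap g between types. With total variance 25 and prevalence 0.3, the variance due to type is 0.3 × 0.7 × g² = 0.21g².
- Type explains 20%: g = √(5/0.21) = 4.9 minutes; shift 0.20 × 4.9 = 1.0 minute, 20% of the 5-minute target.
- Type explains 30%: g = √(7.5/0.21) = 6.0 minutes; shift 0.20 × 6.0 = 1.2 minutes, 24% of the target.

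**5. Cost of adjusting for too much.** With type plus four separate operators in the model and none of them explaining anything, power falls from about 78% to 72% with 32 analysed, and from 93% to 91% with 50.

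**6. What stratification adds.** Four operators assumed, with type explaining 20–30% and operator 10–20% of variance. Power for adjusted v stratified plus adjusted: 86.0% v 87.6% and 94.3% v 95.7% with 32 analysed; 97.7% v 98.2% and 99.6% v 99.7% with 50. The gain is 0.1 to 1.6 points.

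**7. Type I error.** In simulation (within-type SD 4.9, 30% prevalence), the unstratified, unadjusted t-test stays at about 5%. If allocation is stratified but the plain t-test is kept, the error falls to about 3% at a 5-minute gap between types and below 1% at a 10-minute gap.

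**The case against.** The strongest reply is that the gain may be small or nil. Closure time is measured during the procedure, so later dropout should rarely remove it, and most of the 50 may be analysable. At SD 5 the t-test then has about 93% power, above the planned 80%. This stands. The gain becomes material if evaluable numbers fall towards 32 or if the SD of the mixed population is well above 5. Nothing in the documents excludes the second, because they give no SD.

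Four stronger readings are tempting, and the documents do not support them.
- A reader might infer that adjustment is free. It is not: uninformative covariates cost power, and separate operator terms in a small sample cost most.
- A reader might take a 10-minute gap between types and conclude that a 20-point imbalance shifts the result by 2 minutes, 40% of the target. At SD 5 and 30% prevalence, that gap alone would contribute 0.21 × 100 = 21 of a total variance of 25, or 84%, which no figure in the protocol supports.
- A reader might conclude that the randomisation is at fault. The plan is silent on strata; it does not say that allocation is simple, and stratifying adds little once the model adjusts.
- A reader might think the t-test is invalid. Its type I error is unaffected.

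It is also fair to object that type may not be final at allocation. Section B cites perforation as a complication of resection, and section D provides for perforation around the procedure. Any type covariate should therefore be the indication as planned at randomisation.

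**Conclusion.** The point holds as a matter of precision and exposure to chance imbalance, not of validity. The stated primary test discards prognostic information in a heterogeneous, multi-operator sample of at most 50, and a modest model would use it.

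On an assumed SD of 5 with 32 analysed, one type factor gains about 1 to 12 points of power if it explains 5–30% of variance, and costs about 1 point if it explains nothing. A 20-point imbalance in a 30% type, with probability about 16% at 25 per arm, moves the estimate by 1.0–1.2 minutes if type explains 20–30%. All of this rests on assumed SD, explained variance and type mix; the operator figures also assume four endoscopists. The benefit of adjusting for defect size cannot be quantified from the documents, but size is the one defect covariate the plan already records.

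The change is worth making because it is cheap, provided the covariates are few.

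**What to change.** Prespecify in section E, before any outcome data are examined:
- **Primary analysis:** a linear model of closure time on arm, recorded defect size and planned indication at randomisation (resection v existing perforation or fistula). Report the adjusted mean difference in minutes with its 95% CI.
- **Endoscopist:** include only with low-volume operators grouped, by a rule written in advance.
- **Sensitivity analysis:** the unadjusted t-test now planned.
- **Defect size:** state that it is measured before closure begins, because randomisation precedes the procedure and the measurement should not depend on how closure goes.

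Stratifying allocation by planned indication is optional. If it is done, the stratum must be in the primary model, and the plain t-test should be read as conservative.

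The cost is a few sentences of analysis text and one field, planned indication, captured at randomisation. Sample size, endpoint and patient care do not change. If enrolment has started, the analysis change can still be made. The statistical price is the small power loss shown above if the covariates prove uninformative.
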